2.2. Secondary objectives and secondary endpoints

The secondary objectives will be to compare the effect of 2L®ALERG versus placebo on:

- Symptoms of allergy (not corrected by the use of rescue medication),
- Use of rescue medication,
- Evolution of the quality of life (QoL) using 3 daily specific questions included in the patient's diary card: Did you sleep well? Can you work normally? How do you feel?
- Safety (AEs and SAEs).

The secondary endpoints will be:

- Total 5 symptoms score (T5SS) and individual scores of 5 symptoms
- Consumption of rescue medications
- Evaluation of the QoL: AUC (total score of 3 questions of QoL included in the diary card on the Y-axis, and time on X axis) during the entire follow-up period
- Frequency, severity and causality relationship of AEs and SAEs.

[figure not shown]
3. Study design

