6.1. Study procedures

The following demographic data will be collected during the first visit: date of birth, gender, ethnic group, weight, height, smoking habits and alcohol use status.

Medical history, treatment history, concomitant treatments and patient's physical examination will also be documented during V0.

The allergy must be confirmed by positive skin test and/or the presence of IgE for grasses (prick test defined as positive if higher than or equal to half the negative control; IgE are positive if at least class 3 (\geq 3.5 kU/L); these tests must have been made at the latest during the first visit.

A patient diary will be given to each patient.

- For evaluation of the total 5 symptoms score T5SS and rescue medication RS, it is essential that patients note **every day** the symptoms (sneezing, rhinorrhoea, nasal pruritus, itching and/or eye tearing and nasal obstruction) intensity, and the rescue medications, in their patient diary.
- It is also essential that the patient takes note **every day** of his/her QoL by filling in three questions included in his/her diary card: Did you sleep well? Can you work normally? How do you feel?
- It is also imperative that patients note the date of the start of treatment and the date of onset of symptoms.

This patient diary will be given to the patient at each visit, and will be brought back at the next visit, it will be reviewed and validated by the investigator and will be part of the CRF (Case Report Form).

All relevant (related to allergy) concomitant medications (except rescue medications) taken by the patient during the study period will be recorded at each visit in the CRF.

The AEs and SAEs will be recorded at V1 and V2 in order to assess safety.

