A Statistical Analysis Plan (SAP) will be written by the Biostatistician of the CRO in charge of the study. This document will constitute the reference document as far as statistical analyses and statistical methodologies are concerned. It will be approved and signed by the Sponsor and the Principal Investigator before the last patient last visit at the latest.

Study cohorts

Two cohorts will be defined:

- Intention-to-treat (ITT) cohort including all patients having been exposed to at least one dose of the investigational product and in whom at least one efficacy or safety information has been collected after V0.
- Per protocol (PP) cohort including of the ITT having strictly adhered to the protocol and having a compliance between 80% and 120%.

The primary cohort for the statistical analyses will be the ITT cohort.

The patients who will prematurely stop the study will not be replaced.

Statistical methods

The IBM SPSS Statistics (Version 21.0 and eventual upgrades) software will be used throughout statistical analyses.

Missing values will not be replaced, nor extrapolated.

Classical descriptive statistics will be used to describe the patient population at baseline.

The two groups will be compared at baseline using independent Student's t tests for continuous variables and Mann-Whitney's tests, Chi-square tests or Fisher's exact tests for discrete variables.

The superiority of the active treatment over placebo will be demonstrated using an independent Student's test comparing the over-time T5SS (corrected with RM) evolution (AUCs) of the two study groups over the whole treatment period. A P value lower than 5% will be considered statistically significant.

The comparisons between the two study groups in terms of secondary endpoints will be done using the appropriate statistical methods, as they will be described in the SAP. No correction being applied for the multiplicity of endpoints, p values lower than 5% will be considered with caution, as indicative only of potential statistically significant differences between the two groups for the secondary endpoints.

8. Pharmacovigilance and management of adverse events

8.1.Definitions

Adverse events

An adverse event is defined as any untoward medical occurrence in a patient or a participant in a clinical trial, whether or not considered drug related.

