All adverse events encountered during the study, which are observed by the physician or patientreported, will be recorded in the CRF in the section provided for this purpose.

The intensity of adverse events will be quoted as follows:

- 1 = mild
- 2 = moderate
- 3 = severe

For each adverse event, the investigator will have to rule on the causal relationship to the medical product on the following scale: none, possible, probable or certain.

Adverse events or serious adverse events (AEs or SAE)

An AE is considered as SAE when it:

- Results in death,
- Involves life-threatening,
- Results in incapacity or temporary or permanent disability,
- Requires or prolongs patient hospitalization,
- Causes congenital anomaly or neonatal
- Is medically significant (requires care to avoid worsening)

Serious Adverse Reaction (SAR)

A SAR is a SAE considered related to the investigational study product.

Expected adverse reaction or events

An expected adverse event is an event mentioned in the most recent version of the Summary of Product Characteristics (SmPC) for drugs already having a marketing authorization.

The expected effects or serious adverse events will be subject to a delayed declaration by the sponsor to the competent authorities.

Unexpected Serious Adverse Reactions (SUSARs)

Unexpected Serious Adverse Reactions (SUSARs) are events where the nature, severity, frequency or developments are not consistent with product information, with practiced acts and with methods used during the study, as defined in the SmPC.

Unexpected serious adverse events will be subject to a statement within 7 days after their knowledge by the sponsor to the competent authorities.

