8.4. Management of adverse events

All SAEs require filling a SAE report, whether expected or not expected. The investigator must ensure that the information entered on this report is accurate and clear. SAE should be reported immediately to the sponsor (within 24 hours of being highlighted by the investigator).

After being scanned, the SAE report can be sent by e-mail to the following person in charge of pharmacovigilance:

[name] Semaphar sprl [name] Belgium [contact] E-mail address: [contact]

The person in charge of pharmacovigilance will have a copy of the randomization list available in case unblinding is unavoidable after his/her discussion with the investigator.

After receipt of notification of a SUSAR, the sponsor shall declare to the regulatory authorities. Once a year, the sponsor will prepare an annual safety report.

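### Two seriousness criteria in Protocol section 8.1 have no threshold, so a treated or work-limiting allergy episode can be classed as an SAE

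*Protocol*

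**What the plan says.** Section 8.1 of the Protocol starts from a broad definition: "An adverse event is defined as any untoward medical occurrence in a patient or a participant in a clinical trial", whether or not it is thought to be drug related. It then lists what makes such an event serious. Two of the criteria matter here: "Results in incapacity or temporary or permanent disability" and "Is medically significant (requires care to avoid worsening". Intensity is a separate item ("The intensity of adverse events will be quoted as follows", followed by mild, moderate and severe), as is causality.

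Section 8.3 lists three expected adverse events. One is a transient impression of worsening symptoms.

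Section 2.2 makes safety a secondary endpoint: "Frequency, severity and causality relationship of AEs and SAEs". Section 8.4 requires every SAE to reach the sponsor within 24 hours.

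On declaration to the authorities, section 8.1 says under its SUSAR heading: "Unexpected serious adverse events will be subject to a statement within 7 days after their knowledge by the sponsor to the competent authorities". Section 8.4 says: "After receipt of notification of a SUSAR, the sponsor shall declare to the regulatory authorities".

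On the efficacy side, sections 2.1 and 5.3 allow rescue medication, with nasal corticosteroids when first-line options fail or fall short. Section 6.1 has patients record symptoms, rescue medication and three quality-of-life questions every day: "Did you sleep well? Can you work normally? How do you feel".

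**The concern.** The seriousness criteria should pick out a small set of medically grave events. Here two of them overlap with the ordinary course of the disease under study. Every patient has symptomatic grass-pollen allergy and is followed through the pollen season. Section 1.2 itself says that symptoms may limit daily activity and affect work, and rescue treatment is a planned part of the trial.

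If allergy episodes enter the SAE count, part of the safety endpoint repeats what the diary already measures as efficacy. A treatment that reduced symptoms would then also appear to reduce SAEs, and the few other SAEs would sit among disease episodes. If some investigators read the criteria literally and others do not, the count also reflects who did the classifying. Each such report further uses a 24-hour channel meant for serious events.

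**Working it through.** The protocol states no SAE rate, flare rate or rate of lost work days, so there is no figure to reproduce. The check follows one allergy episode through the text.

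1. **Is the episode an adverse event?** The definition in 8.1 is unrestricted, and no section exempts symptoms of the studied allergy. Section 8.3 points the same way by listing symptom worsening as an expected adverse event. That entry describes a transient, treatment-linked impression. The protocol gives the investigator no rule for telling it from a pollen-driven flare.

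2. **Can it meet the disability criterion?** Temporary disability is enough, and incapacity carries no qualifier of degree or duration. The protocol does not say whether a day on which the patient cannot work normally is incapacity. An investigator who says it is does not contradict the text.

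3. **Can it meet the medical-significance criterion?** The event must be medically significant, but the only explanation is the bracket. The bracket names no type of care, and the only outcome to be avoided is worsening. Taking an antihistamine, or moving to a nasal corticosteroid after first-line failure, fits those words on a literal reading.

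4. **Does another passage close the gap?** Section 6.1 collects diary data for the symptom score and collects AEs and SAEs separately at V1 and V2. It also has the investigator review and validate the diary, so the entries are seen. No sentence says whether an entry is efficacy data only, an AE or an SAE. The intensity grade does not decide seriousness.

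5. **Who decides?** The synopsis plans 20 general practitioners for 100 patients, an average of 100 / 20 = 5 patients per centre. Each practitioner must settle the meaning of both criteria alone.

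6. **The 7-day sentence.** Side by side:
   - 8.1 defines a serious adverse reaction as an SAE considered related to the product.
   - The next heading in 8.1 on seriousness and unexpectedness concerns reactions (SUSARs), but its text speaks of events and states no causality condition.
   - 8.4 has the sponsor declare after notification of a SUSAR.

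   The heading and 8.4 agree with each other. The wording of the 7-day sentence does not agree with either.

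**The case against.** The strongest reply is that the text does not make an ordinary flare an SAE. Medical significance heads its criterion, and the bracket only explains it. In the other criterion, temporary qualifies disability, not incapacity. A poor answer to the work question is a quality-of-life score, and no section equates it with incapacity. Diary and safety data are collected separately, and the CRF record of concomitant medication excludes rescue medication. Classification is blinded, and allocation is 1:1 within each centre, so differing thresholds should not favour an arm through knowledge of treatment. Events carry intensity and causality ratings and MedDRA codes, so rhinitis-type events can be tabulated apart. Secondary p values are declared indicative only.

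Most of this stands, and it rules out several stronger readings that a reader might infer:

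- **That every treated flare is an SAE.** The text permits that classification but does not compel it.
- **That most of the 100 patients would have an SAE.** Any such count takes an assumed rate of rescue use and treats each user as a case, which is the point in question.
- **That the SAE endpoint becomes meaningless.** Coding, causality ratings and blinding keep it interpretable, with extra work.
- **That disease flares would flow into 7-day declarations.** Symptom worsening is listed as expected, and 8.1 gives expected events the delayed route. The 7-day sentence also stands under the SUSAR heading.
- **That SAE classification would lead to code breaks.** Section 8.4 reserves unblinding for cases where it is unavoidable, after discussion with the investigator.

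The reply does not supply a threshold for either criterion, or a rule for symptoms of the studied disease. Blinding prevents knowing differences between arms. It does not keep efficacy information out of the SAE count or make centres consistent. Separating events by code afterwards does not undo the 24-hour reports.

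**Conclusion.** The point holds as an over-broad rule that the protocol itself fixes, not as a missing detail that the SAP could supply. Under 8.1 a work-limiting or treated allergy episode can be classed as serious, and centres may differ on the same event. The consequences are a diluted and less consistent SAE component of a secondary endpoint, and avoidable expedited reports. The primary analysis and the sample size are untouched. The size in patients cannot be derived from the document.

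The conclusion rests on a literal reading of the two criteria by at least some investigators, and on the absence of any rule for studied-disease symptoms in the protocol. The mismatch in the 7-day sentence is a smaller, separate wording fault. It is best read as a loose use of the word events.

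**What to change.** In section 8.1, and on the SAE report form where it repeats the criteria:

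1. Limit the disability criterion to persistent or significant disability or incapacity.
2. Limit medical significance to important events that need intervention to prevent one of the other listed serious outcomes.
3. State that diary-scored symptoms and permitted rescue use are not SAEs by themselves. Keep symptom worsening recordable as a non-serious AE, so that the sentence agrees with 8.3. An exemption of these symptoms from AE recording altogether would contradict 8.3 and should be avoided.
4. In the 7-day sentence, replace the reference to unexpected serious adverse events with unexpected serious adverse reactions (SUSARs), so that it matches its own heading and 8.4.

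The cost is a wording amendment, with no change to data collection, analysis or sample size. The small downside is that slightly fewer events go through expedited SAE reporting.

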8.2. Safety endpoints

Collecting data and analysis of safety endpoints described above will be performed by spontaneous statement or during monitoring.

An SAE report form will be attached to the CRF (collecting symptoms, dates, evolution, judgment of causality by the physician, actions taken)

All AEs / SAEs / SARs / SUSARs will be subject to coding in terms of System Organ Class and Preferred Terms, using the latest version of the dictionary MedDRA (Medical Dictionary for Regulatory Activities).

8.3.List of expected AEs

In the framework of this study, expected AEs are those mentioned in the SPC:

- In exceptional cases, it may appear dyspepsia when taken fasted (in this case, the granules will be taken one hour after the meal)
- Difficulties in falling asleep can occur if taken after 16 hours
- As with all homeopathic treatment, print of worsening symptoms can occur, that usually disappears after a few days.

8.4. Management of adverse events

All SAEs require filling a SAE report, whether expected or not expected. The investigator must ensure that the information entered on this report is accurate and clear. SAE should be reported immediately to the sponsor (within 24 hours of being highlighted by the investigator).

After being scanned, the SAE report can be sent by e-mail to the following person in charge of pharmacovigilance:

[name] Semaphar sprl [name] Belgium [contact] E-mail address: [contact]

The person in charge of pharmacovigilance will have a copy of the randomization list available in case unblinding is unavoidable after his/her discussion with the investigator.

After receipt of notification of a SUSAR, the sponsor shall declare to the regulatory authorities. Once a year, the sponsor will prepare an annual safety report.

8.5. Modalities and duration of follow up after the occurrence of adverse events

Given the nature of the study treatment, the follow up shall be two months after the end of the study.

9. Administrative and regulatory aspects

9.1.Right of access to source data

The medical data of each patient will only be transmitted to the sponsor or to any person duly authorized by him, and, as appropriate to relevant health authorities, under conditions ensuring their confidentiality.

The sponsor and the regulatory authorities may request direct access to medical records for verification of procedures and/or clinical trial data, without violating confidentiality and as permitted by laws and regulations.

The data collected during the test will be subject to computerized processing in accordance with the requirements in place in Europe.

9.2. Monitoring

Clinical monitoring will be ensured by the CRO.

A Clinical Research Associate (CRA) will regularly visit the site to carry out quality control of data reported in the CRFs.

The on-site monitoring visits will be organized after appointment with the investigator. The CRA will be allowed to consult:

- CRFs
- Patient's diary cards
- Medical files
- Trial Master File.

9.3.Inspection / Audit

In the context of this study, an inspection or an audit by the regulatory authorities may take place.

The sponsor also reserves the right to audit the investigational centres, either itself or by a third person appointed by him.

9.4. Ethical considerations

Written informed consent:

The entire informed consent process involves giving a participant adequate information concerning the study, providing adequate opportunity for the participant to consider all options, responding to the participant's questions, ensuring that the participant has understand this information, obtaining the participant's voluntary agreement to participate, and continuing to provide information as the participant or situation requires. To be effective, the process should provide ample opportunity for the investigator and the participant to exchange information and ask questions.

The investigator undertakes to inform the patient clearly and after taking time for reflection the patient will sign and date the Inform Consent Form (ICF). The investigator must also sign and date the ICF.

Both documents will be issued on paper in 2 copies so the patient and the investigator can each keep a copy. The original one is for the investigator and will be archived in the Trial Master File.

Ethics Committee:

The sponsor undertakes to submit the study protocol, the diary card and the EQ-5D scale to the prior approval of the Ethics Committee.

Amendments to the protocol: change requests will be sent for authorization in accordance with current legislation, by the sponsor, to the competent authorities. The modified protocol will then undergo an updated version dated.

9.5. Declaration to the competent authorities

An EudraCT application will be submitted to the regulatory authorities (AFMPS/FAGG).

9.6. Financing and insurance

The sponsor shall finance the study and an insurance policy covering the financial consequences of its civil liability in accordance with the regulations.

